**7.7 PROPHYLACTIC MEDICATIONS, TREATMENTS, AND PROCEDURES**

None

**7.8 RESCUE MEDICATIONS, TREATMENTS, AND PROCEDURES**

The participants pain medications can be taken during the study and the use of pain medication will be recorded to determine if resveratrol reduces use of pain medication and/or self reported pain. Non-NSAID pain relievers such

as Tylenol can be used to control pain. If the rescue pain med(s) can't sufficiently control the pain, then the participant will be taken off the study.

## 7.9 PARTICIPANT ACCESS TO STUDY AGENT AT STUDY CLOSURE

Since resveratrol reserveage is an over-the-counter supplement, patients will have full access to product after study concludes.

## 8 ASSESSMENT OF SAFETY

### 8.1 SPECIFICATION OF SAFETY PARAMETERS

#### 8.1.1 DEFINITION OF ADVERSE EVENTS (AE)

Adverse event means any untoward medical occurrence associated with the use of an intervention in humans, whether or not considered intervention-related (21 CFR 312.32 (a)).

#### 8.1.2 DEFINITION OF SERIOUS ADVERSE EVENTS (SAE)

An adverse event or suspected adverse reaction is considered "serious" if, in the view of either the investigator or co-investigator or DSMB, it results in any of the following outcomes: death, a life-threatening adverse event, inpatient hospitalization or prolongation of existing hospitalization, a persistent or significant incapacity or substantial disruption of the ability to conduct normal life functions. Important medical events that may not result in death, be life-threatening, or require hospitalization may be considered serious when, based upon appropriate medical judgment, they may jeopardize the patient or subject and may require medical or surgical intervention to prevent one of the outcomes listed in this definition.

#### 8.1.3 DEFINITION OF UNANTICIPATED PROBLEMS (UP)

Unanticipated problems involve risks to participants or others to include, in general, any incident, experience, or outcome that meets **all** of the following criteria:

- Unexpected in terms of nature, severity, or frequency given (a) the research procedures that are described in the protocol-related documents, such as the IRB-approved research protocol and informed consent document; and (b) the characteristics of the participant population being studied;
- Related or possibly related to participation in the research ("possibly related" means there is a reasonable possibility that the incident, experience, or outcome may have been caused by the procedures involved in the research); and
- Suggests that the research places participants or others at a greater risk of harm (including physical, psychological, economic, or social harm) than was previously known or recognized.

This study will use the Office for Human Research Protections (OHRP) definition of UP.

### 8.2 CLASSIFICATION OF AN ADVERSE EVENT

#### 8.2.1 SEVERITY OF EVENT

The AE grading system used is based on NIH National Cancer Institute's Common Terminology Criteria for Adverse Events (CTCAE) version 5.0 at:

[https://ctep.cancer.gov/protocoldevelopment/electronic\\_applications/ctc.htm#ctc\\_50](https://ctep.cancer.gov/protocoldevelopment/electronic_applications/ctc.htm#ctc_50)

Grade refers to the severity of the AE. The CTCAE displays Grades 1 through 5 with unique clinical descriptions of severity for each AE based on this general guideline:

- **Grade 1** Mild; asymptomatic or mild symptoms; clinical or diagnostic observations only; intervention not indicated.
- **Grade 2** Moderate; minimal, local or noninvasive intervention indicated; limiting age-appropriate instrumental ADL\*.

- **Grade 3** Severe or medically significant but not immediately life-threatening; hospitalization or prolongation of hospitalization indicated; disabling; limiting self care ADL\*\*.
- **Grade 4** Life-threatening consequences; urgent intervention indicated.
- **Grade 5** Death related to AE.

*A Semi-colon indicates 'or' within the description of the grade.*

*A single dash (-) indicates a Grade is not available.*

*Not all Grades are appropriate for all AEs. Therefore, some AEs are listed with fewer than five options for Grade selection. Grade 5 (Death) is not appropriate for some AEs and therefore is not an option.*

Adverse Events	Grade of Adverse Event (CTCAE version 5.0)				
	1	2	3	4	5
Kidney Function					
Creatinine increased	>ULN-1.5x ULN	>1.5-3.0x baseline; >1.5-3.0x ULN	>3.0 baseline; >3.0-6.0x ULN	>6.0x ULN	-
Acute Kidney Injury	-	-	Hospitalization indicated	Life-threatening consequences; dialysis indicated	Death
Hyperkalemia (A disorder characterized by laboratory test results that indicate an elevation in the concentration of potassium in the blood; associated with kidney failure or sometimes with the use of diuretic drugs.)	>ULN-5.5 mmol/L	>5.5-6.0 mmol/L	>6.0-7.0 mmol/L; hospitalization indicated	>7.0 mmol/L; life-threatening consequences	Death
Liver Function					
Alanine aminotransferase increased	>ULN-3.0x ULN if baseline was normal; 1.5 - 3.0 x baseline if baseline was abnormal	>3.0-5.0x ULN if baseline was normal; >3.0 - 5.0 x baseline if baseline was abnormal	>5.0-20.0x ULN if baseline was normal; >5.0 - 20.0 x baseline if baseline was abnormal	>20.0x ULN if baseline was normal; >20.0 x baseline if baseline was abnormal	-
Alkaline phosphatase increased	>ULN-2.5x ULN if baseline was normal; 2.0 - 2.5 x baseline if baseline was abnormal	>2.5-5.0x ULN if baseline was normal; >2.5 - 5.0 x baseline if baseline was abnormal	>5.0-20.0x ULN if baseline was normal; >5.0 - 20.0 x baseline if baseline was abnormal	>20.0x ULN if baseline was normal; >20.0 x baseline if baseline was abnormal	-
Aspartate aminotransferase increased	>ULN-3.0x ULN if baseline was normal; 1.5 - 3.0 x	>3.0-5.0x ULN if baseline was normal; >3.0 - 5.0 x baseline if	>5.0-20.0x ULN if baseline was normal; >5.0 - 20.0 x baseline if	>20.0x ULN if baseline was normal; >20.0 x baseline if	-

	baseline if baseline was abnormal	baseline was abnormal	baseline was abnormal	baseline was abnormal	
Blood bilirubin increased	>ULN-1.5x ULN if baseline was normal; > 1.0 - 1.5 x baseline if baseline was abnormal	>1.5-3.0x ULN if baseline was normal; >1.5 - 3.0 x baseline if baseline was abnormal	>3.0-10.0x ULN if baseline was normal; >3.0 - 10.0 x baseline if baseline was abnormal	>10.0x ULN if baseline was normal; >10.0 x baseline if baseline was abnormal	-
Gastrointestinal Disorders					
Nausea	Loss of appetite without alteration in eating habits	Oral intake decreased without significant weight loss, dehydration or malnutrition	Inadequate oral caloric or fluid intake; tube feeding, TPN, or hospitalization indicated	-	-
Diarrhea	Increase of <4 stools per day over baseline; mild increase in ostomy output compared to baseline	Increase of 4 - 6 stools per day over baseline; moderate increase in ostomy output compared to baseline; limiting instrumental ADL	Increase of >=7 stools per day over baseline; hospitalization indicated; severe increase in ostomy output compared to baseline; limiting self care ADL	Life-threatening consequences; urgent intervention indicated	Death
Platelet count decreased	<LLN- 75,000/mm  ; <LLN -75.0 x 10  /L	<75,000 - 50,000/mm  ; <75.0- 50.0 x 10  /L	<50,000 - 25,000/mm  ; <50.0- 25.0 x 10  /L	<25,000/mm  ; <25.0 x 10  /L	-
Anemia	Hemoglobin (Hgb) <LLN - 10.0 g/dL; <LLN - 6.2 mmol/L; <LLN - 100 g/L	Hgb <10.0 - 8.0 g/dL; <6.2 -4.9 mmol/L; <100 - 80g/L	Hgb <8.0 g/dL; <4.9 mmol/L; <80 g/L; transfusion indicated	Life-threatening consequences; urgent intervention indicated	Death

### 8.2.2 RELATIONSHIP TO STUDY AGENT

The clinician’s assessment of an AE’s relationship to study agent (supplement) is part of the documentation process, but it is not a factor in determining what is or is not reported in the study. If there is any doubt as to whether a clinical observation is an AE, the event should be reported. All AEs must have their relationship to study agent assessed. In a clinical trial, the study product must always be suspect. To help assess, the following guidelines are used.

- **Related** – The AE is known to occur with the study agent, there is a reasonable possibility that the study agent caused the AE, or there is a temporal relationship between the study agent and event. Reasonable possibility means that there is evidence to suggest a causal relationship between the study agent and the AE.
- **Not Related** – There is not a reasonable possibility that the administration of the study agent caused the event, there is no temporal relationship between the study agent and event onset, or an alternate etiology has been established.

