## 8.3 TIME PERIOD AND FREQUENCY FOR EVENT ASSESSMENT AND FOLLOW-UP

The occurrence of an AE or SAE may come to the attention of study personnel during study phone interviews with the study participants or upon review by the DSMB. All AEs including local and systemic reactions not meeting the criteria for SAEs will be captured on the appropriate case report forms. Information to be collected includes event description, time of onset, clinician's assessment of severity, relationship to study drug (assessed only by those with the training and authority to make a diagnosis), and time of resolution/stabilization of the event. All AEs occurring while on study will be documented appropriately in the database regardless of relationship. All AEs will be followed to adequate resolution.

Any PSACH-related medical issue present at the time the participant is screened will be considered as baseline and not reported as an AE. However, if the study participant's condition deteriorates at any time during the study, it will be recorded as an AE. Unanticipated problems will be recorded in the data collection system throughout the study. Changes in the severity of an AE will be documented to allow an assessment of the duration of the event at each level of severity to be performed. AEs characterized as intermittent require documentation of onset and duration of each episode.

The study staff will record all reportable events with start dates occurring any time after informed consent is obtained until 7 (for non-serious AEs) or 30 days (for SAEs) after the last day of study participation. At each study visit, the study staff will inquire about the occurrence of AE/SAEs since the last visit. Events will be followed for outcome information until resolution or stabilization.

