#### 10.4.4 SAFETY ANALYSES

The study DSMB will meet after every 10 patients have successfully completed the full study and all study data has been completed. The DSMB will be presented with all study-duration events (signs/symptoms/co-morbidities) that have been ascertained from all the patients that have completed their participation in the study and will be classified as study-related vs. incidental. The crude rate of the study-related event(s) will be tabulated with one-sided 95% confidence intervals. Additionally, for study-related events that occur in more than 5 patients will be further analyzed to incorporate duration of exposure to study drug.

---

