##### 10.4.7.1 SAFETY REVIEW

The study DSMB will meet after every 10 patients have successfully completed the full study and all study data has been completed. Nonblinded information on all study-duration events (signs/symptoms/co-morbidities) that have been ascertained from all the patients will be classified as study-related vs. incidental.

---

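### The Related and Not Related criteria in 8.2.2 overlap and 10.4.4 tabulates only study-related events, so the planned safety rate can hinge on an unresolved causality label

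*Combined protocol and SAP*

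**What the plan says.** Section 8.2.2 gives three conditions, any one of which makes an adverse event Related. Two concern what is known or plausible about causation: "The AE is known to occur with the study agent, there is a reasonable possibility that the study agent caused the AE". The third asks for timing alone, in the words "or there is a temporal relationship between the study agent and event". Three other conditions, again any one of them, make an event Not Related. The first is a causal judgement: "There is not a reasonable possibility that the administration of the study agent caused the event". The other two turn on timing and on a competing cause, namely that "there is no temporal relationship between the study agent and event onset, or an alternate etiology has been established". Each list is joined by 'or', and nothing says which list prevails when an event satisfies both. The same section says of the clinician's relationship assessment that "it is not a factor in determining what is or is not reported in the study". Section 8.3 adds: "All AEs occurring while on study will be documented appropriately in the database regardless of relationship".

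The analysis is in 10.4.4: "The crude rate of the study-related event(s) will be tabulated with one-sided 95% confidence intervals". Study-related events occurring in more than 5 patients are analysed further for duration of exposure. Neither sentence mentions product, and no rate for all adverse events is planned.

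On who classifies, 8.3 has the relationship assessed by people qualified to diagnose, and 10.6.1 blinds investigators and analysts, with the study coordinator as the exception. Section 10.4.7.1, on the DSMB safety review, says: "Nonblinded information on all study-duration events (signs/symptoms/co-morbidities) that have been ascertained from all the patients will be classified as study-related vs. incidental".

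**The concern.** A rate is only as well defined as the rule that decides what enters its numerator. Here the two causality categories are not exclusive, and the commonest kind of doubtful event falls in both. An example is diarrhoea during dosing in a participant with an established infection. Diarrhoea is an expected event in the table in 2.3.1 and the timing fits, so it is Related. Another cause is established, so it is Not Related.

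Two careful assessors could follow the text and produce different safety tables from the same data. The label also decides whether an event type receives the exposure analysis. Since 10.4.4 gives no all-event rate and no split by product, no planned summary is free of the label. In a placebo-controlled crossover, the comparison of events on each product is the natural safety summary, and it is not specified.

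**Working it through.** **1. Do the definitions overlap?** Four yes/no conditions come from 8.2.2: K, known to occur with the agent; P, reasonable possibility of causation; T, temporal relationship; A, alternate etiology established.

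- Related = K or P or T.
- Not Related = (not P) or (not T) or A.

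There are 2^4 = 16 combinations:

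- Only Related needs P and T and not A, with K free: 2 combinations.
- Only Not Related needs not K, not P and not T, with A free: 2 combinations.
- Neither would need P both true and false: 0 combinations.
- Both: 16 − 2 − 2 − 0 = 12 combinations.

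Some of the 12 may not arise in practice. Suppose an established alternate etiology rules out a reasonable possibility (drop the 4 combinations with P and A). Suppose also that a reasonable possibility requires a temporal relationship (drop the 2 with P, not T, not A). All 6 dropped combinations were in the overlap, so 12 − 6 = 6 of the remaining 10 still meet both definitions. These 6 have no reasonable possibility of causation, but either fit in time or are known effects of the agent. The diarrhoea example is one of them.

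**2. Does the overlap reach the analysis?** Section 10.4.4 speaks of study-related versus incidental events and does not cite 8.2.2. If those terms mean Related and Not Related, they inherit the overlap. If they do not, the documents do not define them. Either way, the numerator is not fixed.

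**3. How far could the rate move?** The plan states no event rate, so there is no figure of its own to reproduce. The inputs for an illustration are:

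- n = 30, from 4.1 and 10.5 (10.6.1 says one hundred, a separate conflict).
- Assumed: 8 patients have a given event, and 5 of the 8 have both a temporal relationship and an established alternate etiology. The count is then 8 if those 5 are called Related, or 8 − 5 = 3 if not.
- Assumed: the one-sided limit is an upper limit, computed exactly (Clopper-Pearson). Section 10.4.4 names neither side nor method.

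Rate = x/n. Upper bound = 95th percentile of Beta(x + 1, n − x).

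| Patients counted as study-related | Rate | Upper bound | More than 5 patients? |
|---|---|---|---|
| 8 | 8/30 = 26.7% | 43.0% | yes |
| 3 | 3/30 = 10.0% | 23.9% | no |
| 6 | 6/30 = 20.0% | 35.7% | yes |
| 5 | 5/30 = 16.7% | 31.9% | no |

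The first two rows are the same data under the two labels. The last two show that relabelling one patient takes an event below the trigger for the exposure analysis. A rate for all adverse events would be 8/30 under either label in the first pair.

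**The case against.** The strongest reply is that nothing is lost from oversight. All events are documented whatever their cause (8.3), the DSMB hears of all of them (8.4.1) and reviews safety on each arm (8.6), and the halting and discontinuation rules in 8.5 carry no relatedness condition. This stands. An event labelled Not Related leaves only one rate table and its exposure follow-up, so a reader who inferred that safety events disappear would be going beyond the text.

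A reader might also infer that unblinded judgement decides the published rate. The documents do not support that. The word nonblinded occurs only in the DSMB review in 10.4.7.1; the parallel text in 10.4.4, which contains the rate, does not use it. Sections 8.3 and 10.6.1 together imply a blinded clinician's assessment, and 10.6.3 keeps other team members blinded when the code is broken for the DSMB. What stands is narrower: the plan does not say which of the two classifications feeds the rate.

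Third, 8.2.2 presents its criteria as guidelines and says the study product is always to be suspected. That leans doubtful cases towards Related, but it is not stated as a precedence rule, and the alternate-etiology limb pulls the other way.

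Fourth, restricting one table to related events does not plainly contradict the statement in 8.2.2 about what is reported, since that section concerns documentation and reporting of events. I do not rely on a contradiction. Finally, 10.4.10 allows individual data to be tabulated, but only as needed; that is not a prespecified summary.

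**Conclusion.** The point holds in limited form. The categories overlap on their wording, and the only planned safety rate depends on a label that the plan neither ties to those categories nor assigns to a named assessment. The rate and the more-than-5-patients trigger can therefore change without any change in the data. The primary efficacy analysis is not touched.

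The size is unknown. The difference of 26.7% against 10.0% rests on assumed counts and on an exact upper bound at n = 30. It shows what the wording permits, not what will happen. One could draw a larger swing by starting from the 33% placebo rate of nausea and diarrhoea in 2.3.1 and relabelling every case, which takes 10 of 30 to 0 of 30. The documents do not support that as a realistic case. It would need an alternate etiology to be established for all 10 participants, and 2.3.1 itself attributes the high background in that 52-week dementia study to another drug.

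**What to change.** Three changes of wording and one table:

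- **10.4.4:** tabulate all adverse events, whatever the causality, by product taken at onset (resveratrol, placebo, washout), with related events as a secondary column. The main safety rate then no longer depends on the label.
- **8.2.2:** make the two categories mutually exclusive, or state which limb takes precedence when a temporal relationship and an established alternate etiology coexist. Use the same terms in 10.4.4 and 10.4.7.1.
- **10.4.4 and 10.4.7.1:** state that the related column uses the blinded clinician's assessment recorded under 8.3, and not the DSMB's classification on nonblinded information.

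No new data are needed. Time of onset and relationship are already collected under 8.3, and the product sent to each participant is logged under 6.2. The halting and discontinuation rules do not change.

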### 8.2.3 EXPECTEDNESS

The DSMB will be responsible for determining whether an AE is expected or unexpected. An AE will be considered unexpected if the nature, severity, or frequency of the event is not consistent with the risk information previously described for the study agent.

## 8.3 TIME PERIOD AND FREQUENCY FOR EVENT ASSESSMENT AND FOLLOW-UP

The occurrence of an AE or SAE may come to the attention of study personnel during study phone interviews with the study participants or upon review by the DSMB. All AEs including local and systemic reactions not meeting the criteria for SAEs will be captured on the appropriate case report forms. Information to be collected includes event description, time of onset, clinician's assessment of severity, relationship to study drug (assessed only by those with the training and authority to make a diagnosis), and time of resolution/stabilization of the event. All AEs occurring while on study will be documented appropriately in the database regardless of relationship. All AEs will be followed to adequate resolution.

Any PSACH-related medical issue present at the time the participant is screened will be considered as baseline and not reported as an AE. However, if the study participant's condition deteriorates at any time during the study, it will be recorded as an AE. Unanticipated problems will be recorded in the data collection system throughout the study. Changes in the severity of an AE will be documented to allow an assessment of the duration of the event at each level of severity to be performed. AEs characterized as intermittent require documentation of onset and duration of each episode.

The study staff will record all reportable events with start dates occurring any time after informed consent is obtained until 7 (for non-serious AEs) or 30 days (for SAEs) after the last day of study participation. At each study visit, the study staff will inquire about the occurrence of AE/SAEs since the last visit. Events will be followed for outcome information until resolution or stabilization.

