## PROTOCOL SUMMARY

[figure not shown]
Title:	Trial of Resveratrol for Pseudoachondroplasia Pain
Précis:	This is a cross over designed study to determine if self-administered oral resveratrol (90 days) can dampen joint pain for individuals with pseudoachondroplasia compared to placebo (90 days) as measured by daily pain logs.
Objectives:	To determine if resveratrol reserveage liquid lessens joint pain in individuals with pseudoachondroplasia.
Endpoint	Self-reported pain as ascertained by a 11-point pain scale from 0 to 10.
Population:	Pseudoachondroplasia patients aged 18 to 70 yrs (details below)
Phase:	IIA ("proof of concept" study)

**Number of Sites enrolling participants:** 1  
**Description of Study Agent :** Resveratrol Reserveage liquid super berry blend 225 mg + Pro-longevity factors blend 130 mg including **125 mg trans-resveratrol**

**Study Duration:** 5 yrs  
**Participant Duration:** 210 days

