## 4 STUDY DESIGN AND ENDPOINTS

### 4.1 DESCRIPTION OF THE STUDY DESIGN

The study has a 2x2 crossover design. Participants will take either the placebo or resveratrol for 90 days followed by a 30 day washout period and the placebo or resveratrol for the last 90 days. 30 day washout period was chosen in order to eliminate any carry over from resveratrol as it is recommended to avoid resveratrol 2 weeks prior to surgery suggesting that carry over could potentially be as long as 2 weeks (<http://www.webmd.com/vitamins-supplements/ingredientmono-307-resveratrol.aspx?activeingredientid=307>; <http://ww5.komen.org/BreastCancer/Resveratrol.html>). Participants will be mailed a 30 or 90 day (for international participants) supply of placebo or resveratrol which they will receive 5 days before the end of each 30 day period (not applicable for international participants). Participants will keep daily pain log of pain and activity levels during the entire 210 day study period. We recognize that this is a long period of time however this population is highly motivated because 1) their pain is not systematically treated, 2) currently available over the counter NSAIDs, frequently used to control pain, cause gastrointestinal issues when used for prolonged periods and 3) participants reached through Little People of America and the PSACH facebook page are actively seeking solutions to control pain. This is being co-ordinated by a single center and will enroll 30 PSACH individuals. Because this is a rare condition, participants from 18 years - to 70 years will be enrolled.

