### 5.4.2 HANDLING OF PARTICIPANT WITHDRAWALS OR TERMINATION

Participants who choose to withdraw or are withdrawn due to an AE or exclusion criteria must return the unused portion of study materials to the study coordinator. **All mailing/communication costs will be paid by the study.**

All participants withdrawn/discontinued will be followed for 1 month to make sure that no AEs have developed after withdrawal from the study. If a participant was withdrawn due to AEs, they will be advised to seek medical help with their primary care physician. Those costs are not covered by this study.

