### 6.1.9 DURATION OF THERAPY

90 days each of either placebo or resveratrol, with a month (30 days) of no medication in between the crossover administration.

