## 7 STUDY PROCEDURES AND SCHEDULE

### 7.1 STUDY PROCEDURES/EVALUATIONS

#### 7.1.1 STUDY SPECIFIC PROCEDURES

- All potential participants will submit photos to confirm their PSACH diagnosis either by directly depositing photos into a secured encrypted server or via US mail (to be scanned and put into our secure data base and subsequently shredded).
- Medical history will be obtained by interview to confirm diagnosis of PSACH and to exclude those taking exclusion medications resveratrol, blood thinners, lovastatin, ketoconazole, itraconazole, fexofenadine, triazolam, Alfentanil, Cyclosporine, Dihydroergotamine, Dofetilide, Ergotamine, Fentanyl, Flibanserin, Oxycodone, Pimavanserin, Pimozide, Quinidine, Saquinavir, Sirolimus, Tacrolimus, Temsirolimus, Theophylline, Tizanidine, Thioridazine, Fosphenytoin, Phenytoin, or Warfarin. This information will be ascertained by the study staff over the phone and the participants will be asked to read the names of the medications and the dosages off the medicine containers. Information on medications will be collected for All medications the participant is on (both prescription and OTC). Exclusions will be made if any of the medications mentioned above are being used.
- Pain will be assessed to ensure that participants have pain to enroll in the study.
- For this 2X2 crossover design with two periods, patients will be randomized to one of two sequences, resveratrol/placebo or placebo/resveratrol. Those randomized to resveratrol/placebo will be given resveratrol in the first period and placebo in the second and vice versa for those randomized to the placebo/resveratrol sequence. Randomization will be carried out by our biostatistician so that investigators evaluating outcomes, along with participants, are blinded.
- Once enrolled into the study and randomized, a parcel will be mailed to the participants including all study materials including first month's study drug supply, study forms and pain logs.
- Monthly phone calls will be used to assess of adherence to protocol and will be logged into the study logbook by study staff. These phone calls will also include ascertainment of any changes to medications and diagnosis of any new health condition or pregnancy.
- Patient-reported daily pain logs will be mailed or emailed to study co-ordinator on a monthly basis.

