7.3.4 FINAL STUDY VISIT

**Final Study Visit (Visit 8, Day 210 +/- 5 working days)**

- Inform patient that they have completed the study.
- Record adverse events as reported by participant to study co-ordinator. Study coordinator will ask about gastrointestinal health, any bleeding events and unusual bruising. PI will follow up with participant to assess the adverse events and determine whether to terminate participation.
- Record participant’s adherence to treatment protocol.
- Inquire about any medication and health condition changes.
- Participants will be asked to complete blood draw from their local facility at our cost to assess kidney function, liver function and blood cell count. The complete metabolic panel includes analysis of renal function [blood urea nitrogen (BUN), creatinine], liver function [total bilirubin, alanine aminotransferase (ALT), alkaline phosphatase (ALP), and aspartate aminotransferase (AST)], glucose, electrolytes [calcium, sodium, potassium, carbon dioxide (bicarbonate), chloride], protein [albumin, total protein]. The complete blood count (CBC) includes analysis of red blood count, hemoglobin, hematocrit, white blood cell count, platelet count. Platelet count below 50,000 per µl in CBC which indicates increased bleeding risk will result in removal from the study.
- Administer HRQoL instrument.
- Request participant to mail back or email their pain log and mail back any unused medication or email a photo of the empty bottle. The data from the pain logs will be compiled and analyzed at the start and end of the two treatment periods (on days 0, 90, 120, and 210).
- Ask participants about which medication, resveratrol or placebo, they think they were taking during the last 90 day period (evaluation of the success of blinding).

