**Post Study Visit (Visit 9, Day 240 +/- 5 working days)**

- Participants will be queried regarding any AE/SAE.

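### Section 8.3 stops recording non-serious adverse events 7 days after an undefined last day of participation, which conflicts with the Day 240 call and the 1-month follow-up after withdrawal

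*Combined protocol and SAP*

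**What the plan says.** Section 8.3 sets the recording period by date of onset: from consent "until 7 (for non-serious AEs) or 30 days (for SAEs) after the last day of study participation". It does not say which day is the last. The protocol points to Day 210:

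- The summary gives "Participant Duration: 210 days".
- The instruction for Visit 8 (Day 210) is "Inform patient that they have completed the study".
- Visit 9 (Day 240) is labelled as post-study.

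Other places use a longer follow-up for adverse events in general:

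- At Visit 9, "Participants will be queried regarding any AE/SAE". The schedule of events (7.3.7) also marks adverse event ascertainment at that visit.
- Under 5.4.2, withdrawn participants "will be followed for 1 month to make sure that no AEs have developed after withdrawal from the study".
- Section 7.3.5, written for early termination of the study, plans a further contact after 30 days covering both serious and non-serious events.

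Section 4.1 justifies the 30-day washout by pre-surgery advice, "suggesting that carry over could potentially be as long as 2 weeks".

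**The concern.** The protocol asks a question at Day 240 and has no agreed rule for the answer. Suppose a participant who completes the trial reports bruising that began on Day 222. Visit 9 elicits it, but its onset lies outside the period in 8.3. One member of staff may record it and another may not, and each could cite the protocol.

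This matters because the events of interest here are mostly of the kind that would be non-serious. The risk table in 2.3.1 lists nausea and diarrhea as expected, and the coordinator asks specifically about gastrointestinal health, bleeding and bruising. Non-serious events also have consequences in the plan. Grade 1 and 2 events count toward the study-wide halting criteria in 8.5, with thresholds as low as three events. Study-related events enter the crude rates in 10.4.4. With about 30 participants, one mild event recorded or not recorded can change a count.

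The cut-off also falls differently in the two sequences. After period 1 the whole washout is covered, because each visit asks about events since the previous visit. After period 2 only 7 days are.

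**Working it through.** This is calendar arithmetic; no power formula applies.

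**Inputs.** Section 6.1.9: "90 days each of either placebo or resveratrol, with a month (30 days) of no medication in between the crossover administration". Section 7.1.1: "patients will be randomized to one of two sequences, resveratrol/placebo or placebo/resveratrol". Recording windows of 7 and 30 days (8.3). Carry-over of up to 14 days (4.1). Visits 8 and 9 each within 5 working days of Day 210 and Day 240, taken here as about 7 calendar days.

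**The plan's own timeline.** 90 + 30 + 90 = 210 days, which matches the stated duration. 210 + 30 = 240, which matches Visit 9.

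**Last day read as Day 210**

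- Non-serious window ends: 210 + 7 = Day 217.
- Serious window ends: 210 + 30 = Day 240.
- Days the Visit 9 call asks about but 8.3 does not cover: 240 − 217 = 23 (Days 218 to 240). With the visit tolerance, 233 − 217 = 16 to 247 − 217 = 30.
- Possible carry-over ends: 210 + 14 = Day 224. Uncovered: 224 − 217 = 7 of 14 days.
- After withdrawal, counting from the withdrawal date and taking a month as 30 days: 30 − 7 = 23 days followed but not covered.

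**Last day read as Day 240**

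- The windows end at 240 + 7 = Day 247 and 240 + 30 = Day 270.
- The Day 240 conflict disappears, but no contact is scheduled after Visit 9.
- The conflict with 5.4.2 is not resolved by this reading alone, since that month runs from withdrawal.

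**Off-drug recording of non-serious events, by sequence (Day 210 reading)**

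| Sequence | After resveratrol | After placebo |
|---|---|---|
| Resveratrol first | 30 days (washout) | 7 days |
| Placebo first | 7 days | 30 days (washout) |

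The ratio after resveratrol is 30/7 = 4.3. Total recording time is the same in both sequences (to Day 217).

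**Effect on a pooled comparison.** I assume 30 participants (4.1, 10.5; section 10.6.1 gives one hundred) split equally, which the protocol does not state.

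- After resveratrol: 15 × 30 + 15 × 7 = 555 person-days.
- After placebo: 15 × 7 + 15 × 30 = 555 person-days.

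The two agree whenever the sequences are equal in size and complete, whatever the total. As an illustration of unequal completion, take 16 resveratrol-first and 11 placebo-first completers: 16 × 30 + 11 × 7 = 557 against 16 × 7 + 11 × 30 = 442.

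**The case against.** Different windows for serious and non-serious events are a permissible choice, and 8.3 contains no instruction to discard a reported event. Other text leans toward recording: 8.2.2 says to report when in doubt, and 8.4.1 has forms completed as events come to light and the DSMB told of every adverse event. All of this stands. A reader might infer that events reported at Day 240 will certainly be dropped, and the documents do not show that. They do leave a dated cut-off in 8.3 that nothing else withdraws, so the outcome depends on which section staff follow.

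The 2-week carry-over is only a stated possibility, drawn from pre-surgery advice. Nothing in the protocol shows that new events begin 8 to 14 days after stopping, and the gastrointestinal effects it cites arose at 0.5 to 5 g per day against 125 mg here. So the days can be counted, but the number of missed events cannot be estimated.

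A reader might also infer that completers and withdrawn participants are treated differently. They are not: both are followed for about 30 days, and 8.3 applies to both. The mismatch is between follow-up and recording, and it is the same for each group.

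Finally, Visit 9 may fall at about Day 233, before the serious-event window closes at Day 240. This is a small point, because that window concerns onset and not the date of contact.

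**Conclusion.** The inconsistency is real and should be corrected. Taking Day 210 as the last day, 8.3 leaves 23 days of non-serious events that the Day 240 call asks about outside the recording rule. It also leaves out 23 of 30 days after withdrawal, and 7 of the up to 14 days of carry-over that the protocol allows for.

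It is tempting to conclude that resveratrol event counts will be too low relative to placebo. The documents do not support that. The shorter window after resveratrol in one sequence is matched by the shorter window after placebo in the other, and with equal, complete sequences the off-drug person-days are identical. An imbalance needs unequal sequence sizes or dropout, and no by-sequence analysis of adverse events is planned. The harm is late non-serious events lost or captured inconsistently, which weakens the halting counts and crude rates. The pain endpoint is not affected.

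The day counts rest on the Day 210 reading and on a month taken as 30 days.

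**What to change.** In 8.3, define the last day of study participation and use one recording window for serious and non-serious events alike: onset up to 30 days after the later of the last dose and the last on-study visit (Visit 8 or withdrawal). Apply it to completers and withdrawn participants, and bring 5.4.2, 7.3.5, Visit 9 and the schedule of events into line.

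Time Visit 9 from the actual Visit 8 date: 30 days, plus up to 5 working days and not minus. The call then falls at or after the end of the window. If Visit 8 is late, at about Day 217, the window ends at about Day 247 and Visit 9 moves with it.

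Simpler versions do not work. Anchoring to the last dose alone would close the window at Day 180 for someone who stops product at Day 150 but stays on study to Day 210. A fixed Day 240 call is too early when Visit 8 is late. A 14-day window would cover the possible carry-over (to Day 224) but leave 16 days before the call, and 30 against 14 days after resveratrol between the sequences. With the 30-day window both sequences have at least 30 days, and no possible carry-over days are uncovered.

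The cost is a short rewording and a few more unrelated events to record. No new visit or procedure is needed.
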